A Megastudy of Single-Session Interventions for Depression (Includes analysis plan and
consent form) March 8, 2025

Protocol

Design

Participants will be randomly assigned to one of 13 conditions, with even odds of allocation, except that the passive control condition will have 3X odds of allocation. Researchers will use Qualtrics's "evenly present elements" feature to ensure each condition gets a roughly equal number of participants.

Procedure

1. **Screen.** Participants will be asked to complete the Patient Health Questionnaire (9-item, PHQ-9) to assess eligibility. Next, eligible participants will be asked to consent to participate in the study.
2. **Baseline session.** Participants who consented will immediately begin the first study session, starting with a baseline well-being questionnaire. Next, they will be randomly allocated to one of the 11 experimental SSI conditions, an active comparison SSI condition, or a passive control condition. After they complete the condition to which they were randomized, they will respond to some of the baseline measures again, as well as measures of SSI satisfaction.
3. **Follow-up.** Four weeks later, participants will be invited to a follow-up survey, in which they will complete the baseline well-being survey again.

Participants will be compensated directly after completing each study session. If participants drop out of the baseline session after randomization, they will still be invited to complete the follow-up survey. After each study session, participants will be offered access to a list of online mental health resources (see <https://osf.io/wz5u6>).

Measures

See the "Megastudy Measures" document (<https://osf.io/76cfy>) for information on measures, and the "Timepoints of megastudy measures" document (<https://osf.io/hn83p>) for information on measurement timepoints.

To measure depressive symptoms, researchers will use the reliable and valid Patient Health Questionnaire (9-item). Researchers will consider a change in PHQ-9 score of 5 or greater to be clinically meaningful (Kroenke, 2012). To measure agency, researchers will use the Pathways Subscale of the State Hope Scale, a reliable and valid three-item self-report measure of one's perceived ability to generate plans and work toward goals. To measure hopelessness, researchers will use the reliable 4-item Beck Hopelessness Scale. Researchers will measure depression change expectancies using three items from the

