1. For each experimental SSI, researchers hypothesize that participants assigned to the SSI will report a different extent of change in depressive symptoms from baseline to four-week follow-up than participants in the active comparison condition.
2. For each SSI, researchers hypothesize that participants assigned to the SSI will report a different extent of change in each secondary well-being outcome (agency, hopelessness, depression change expectancies, readiness for change, frequency of positive actions and thoughts) compared to participants in the passive control. researchers will compare change in all outcomes from baseline to four-week follow-up, as well as from baseline to immediate post-intervention for outcomes collected at all three timepoints.
3. For each experimental SSI, researchers hypothesize that participants assigned to the SSI will report a different extent of change in each secondary well-being outcome (from baseline to week four or baseline to post-intervention) than those assigned to the active comparison condition.
4. For each experimental SSI, researchers hypothesize that participants will rate the SSI as differently acceptable than the active comparison SSI according to CEQ scores, star ratings, and rate of Aha! Moments.
5. We hypothesize that participants who expect they can improve their depression more at baseline will show a different change in depressive symptoms from baseline to week four.
6. We hypothesize that, on average, the SSIs will be more effective at improving all well-being outcomes (from baseline to week four or baseline to post-intervention) than the passive control.

We do not make any specific hypotheses about which SSIs will be more effective or acceptable than others.

Statistical Analysis Plan

Inclusion criteria

Participants will need to be at least 18 years old, be able to read and write fluently in English, and have enough access to the internet to complete two sessions over four weeks. They must also score at least 10 on the PHQ-9 screen (suggesting moderate depression) and pass the bot check (<https://osf.io/kba7v>) during the screen (Kroenke et al., 2001).

All participants who are randomized to an experimental condition (and therefore completed all baseline measures) will be included in analyses. If a participant begins a survey multiple times, researchers will only keep data from the first time.

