Please see the measures document (<https://osf.io/76cfy>) and the data cleaning script (<https://osf.io/jpk38>) for details on measures and recoding. Before sharing the study data, researchers will remove any potentially identifiable information, included in written response items. Deviations from this pre-registration will be documented.

References:

Primary analysis

Researchers will use a mixed-effects linear regression model to test if depressive symptoms decrease more from baseline to four-week follow-up in each of the 12 active conditions compared to the passive control condition. Timepoint is a three-level factor (i.e., baseline, post-test, and week 4 follow up). The model will include a participant identifier as a random intercept.

Using the “lme4” and “lmerTest” packages in R, this analysis will take this form:

```
lmer(depressive_symptoms ~ timepoint * condition + (1|participant_id))
```

Using lmerTest’s default, p-values will be calculated using Satterthwaite’s method for denominator degrees of freedom.

Secondary analyses (matching the hypotheses above):

1. To test if each experimental SSI changes PHQ-9 scores differently from the active comparison SSI, researchers will redo the main analysis, except using the active comparison condition as the comparator.

2. To test if each SSI changes secondary well-being outcomes to a different extent than the passive control, researchers will replicate the primary analysis for each secondary outcome. For outcomes measured at three timepoints, researchers will compare baseline to each timepoint.
3. To test if each experimental SSI changes secondary well-being outcomes to a different extent than the active comparison SSI, researchers will redo analysis #2, but instead use the active comparison SSI as the comparison condition.
4. To test if each experimental SSI differs in acceptability from the active comparison SSI, researchers will conduct a linear regression model testing between-group differences in intervention acceptability for each acceptability outcome at each timepoint the outcome was collected. For these analyses, researchers will drop data from the passive control because it does not make sense to compare satisfaction with a mental health intervention to satisfaction with an educational program about trout.

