5. To test if participants who expect that they can change their depression more at baseline will show a different reduction in depressive symptoms from baseline to week four, researchers will run a linear mixed-effects regression model with depressive symptoms as the DV, timepoint, baseline depression expectancies, and the interaction between the two as predictors, and a participant identifier nested in experimental condition as a random intercept.
6. To test if, on average, the SSIs will change each outcome differently than the passive control, researchers will re-run the main analysis with *experimental condition* re-coded into a two-level factor in which any of the 12 active SSIs will be coded as “active.” The random intercept, participant ID will be nested within experimental condition. For outcomes measured at three timepoints, researchers will compare the baseline to each timepoint

Sensitivity analyses:

1. Researchers will re-run the primary analysis with demographic covariates: age, gender, disability, race, education, relationship status, political party, employment status, household income, and perceived socioeconomic standing (Social Ladder).
2. Researchers will re-run the primary analysis with demographic and baseline mental health covariates: age, gender, disability, race, education, relationship status, political party, employment status, household income, perceived socioeconomic standing (Social Ladder), baseline depression change expectancies, baseline

positive actions and thoughts, baseline readiness for change, baseline agency, and baseline hopelessness.

3. Researchers will test for differential attrition across conditions and by the interaction of condition and each covariate. If researchers find evidence for differential attrition, researchers will conduct a sensitivity analysis re-running primary and secondary analyses accounting for differential attrition using inverse probability weighting. See the analysis script (<https://osf.io/5eya3>) for details.

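### The post-session acceptability comparison leaves out people who quit mid-SSI, so an SSI with more dislike-driven exits can look more acceptable than it is

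*Combined protocol and SAP*

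**What the plan says.** Secondary hypothesis 4 is that participants will "rate the SSI as differently acceptable than the active comparison SSI according to CEQ scores, star ratings, and rate of Aha! Moments". To test it, Secondary analyses item 4 states that "researchers will conduct a linear regression model testing between-group differences in intervention acceptability for each acceptability outcome at each timepoint the outcome was collected", with the passive control left out. This gives 11 comparisons per acceptability outcome.

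The timing is in Protocol, Procedure, item 2: "After they complete the condition to which they were randomized, they will respond to some of the baseline measures again". The satisfaction questions belong to that same block, which comes once the condition is finished. The same section foresees early exit: "If participants drop out of the baseline session after randomization, they will still be invited to complete the follow-up survey". That follow-up is described only as a survey "in which they will complete the baseline well-being survey again".

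Three other parts of the Statistical Analysis Plan bear on this:

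- Inclusion criteria: "All participants who are randomized to an experimental condition (and therefore completed all baseline measures) will be included in analyses".
- Missing data handling: a scale with more than 33% of its items missing counts as wholly missing and is not imputed. The reason given is a property of linear mixed models for longitudinal data.
- Sensitivity analyses, item 3: if differential attrition is found, primary and secondary analyses are re-run "accounting for differential attrition using inverse probability weighting", with details in an external script.

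**The concern.** A participant who quits partway through an SSI has no post-session Credibility/Expectancy Questionnaire (CEQ) score, star rating or Aha! response, and so contributes nothing to the post-session regression. Nominal inclusion of everyone randomised does not change that. The comparison is then conditional on an event after randomisation that may itself reflect dislike of the SSI.

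The reason given for not imputing does not reach this analysis. For the PHQ-9, a mixed model can use a participant's baseline score when a later one is missing. Acceptability has no baseline value, and item 4 is a cross-sectional linear regression.

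At stake is the answer to secondary hypothesis 4. Quitting can be a direct sign of low acceptability, yet here it removes low ratings and can raise the mean of the SSI that people left. The primary PHQ-9 analysis is not affected.

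**Working it through.** **What the plan states.** There is no figure for acceptability or for in-session dropout to reproduce. The arm size comes from the Sample Size section: 12 × 500 + 1,500 = 7,500, as stated. The PHQ-9 figure also reproduces: (1.960 + 1.282) × √(1/500 + 1/1,500) = 0.167, below the stated d = 0.17. I use 500 per SSI arm.

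**Assumptions for the illustration (none from the documents).** Two SSIs have identical true star ratings: a normal with mean 3.7 and SD 1.0, rounded to 1–5 (after rounding, mean 3.66 and SD 0.97). Dropout is logistic in the rating, with slope 0.5, 1.0 or 1.5, so the odds of quitting rise about 1.6, 2.7 or 4.5 times per star lower. The intercept is set to give the stated dropout in each arm.

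**Formulas.** Bias = mean rating of raters in the high-dropout arm − mean rating of raters in the active comparison. SE = √(s₀²/n₀ + s₁²/n₁), where n is 500 × (1 − dropout). False rejection is the chance that a two-sided 5% test rejects at z = bias/SE.

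**Worked case: 5% vs 15%, slope 1.0.** The rater means are 3.710 and 3.796, so the bias is 0.086. SE = √(0.942²/475 + 0.906²/425) = 0.0616, z is about 1.4, and false rejection is about 29%.

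| Dropout (comparison vs SSI) | Bias in stars, slopes 0.5 / 1.0 / 1.5 | False rejection |
|---|---|---|
| 5% vs 10% | 0.02 / 0.04 / 0.06 | 7% / 11% / 16% |
| 5% vs 15% | 0.05 / 0.09 / 0.11 | 11% / 29% / 47% |
| 5% vs 25% | 0.09 / 0.17 / 0.21 | 29% / 75% / 94% |

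With slope 0, or with equal dropout that is similarly related to rating in both arms, the bias is 0 and rejection is 5%.

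**Second model.** Let latent acceptability be N(0,1), with correlation ρ to a latent variable that decides exit. The completer mean is ρ·φ(z_q)/(1 − q) for dropout q. For 20% vs 5% the difference is ρ × (0.350 − 0.109) = 0.241ρ, that is 0.12 SD at ρ = 0.5 and 0.19 SD at ρ = 0.8. This is the same pattern.

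**What weighting can do.** I simulated this second model at 20% vs 5%, weighting on one baseline covariate correlated 0.3–0.5 with acceptability. The bias falls only from about 0.12 to 0.09–0.12 SD (ρ = 0.5) and from 0.19 to 0.16–0.18 SD (ρ = 0.8).

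**Would the weighting be triggered?** A pairwise test of exit rates with 500 per arm has 49% power for 5% vs 8%, 85% for 5% vs 10%, and over 99.9% for 5% vs 15%.

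**The case against.** **A reader might infer that the plan restricts acceptability to finishers.** The text does not say so. All randomised participants are nominally included, item 4 covers every timepoint at which the outcome was collected, and people who leave early are invited to follow-up. A week-4 acceptability item is possible. The Procedure section names only the well-being survey there, and the timepoints document is external. This stands as a limit on the claim, but a week-4 item would not repair the post-session comparison.

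**A reader might also infer that the weighting would not run, or that it uses only condition and baseline covariates.** Neither is established. Those terms are stated for the attrition test; the weight model is in the external script. If attrition covers in-session exit, a large gap would almost certainly trigger the weighting. Where the trigger could easily miss (5% vs 8%), the star model gives a bias of only 0.01–0.04 stars. What survives is narrower: weighting redistributes observed ratings, and on baseline data it cannot recover dislike that arose during the SSI.

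**The large figures need strong assumptions.** At 5% vs 25% with the steepest slope, about 92% of would-be 1-star raters and 3% of 5-star raters quit. Payment follows completion of each session, which encourages finishing. This stands, and the 5% vs 10% row matters as much as the others.

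**Ratings among those who rated are a legitimate target.** Hypothesis 4 is about how participants rate the SSI. That is fair, but the plan does not label the comparison so. It tests attrition across conditions but does not present completion as an acceptability result.

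**Conclusion.** The concern holds as a conditional one. Under the plan as written, people who exit mid-SSI fall out of the post-session acceptability regression. An SSI with more exits is favoured if those exits are related to dislike. Under the star-rating assumptions the size runs from negligible (0.02 stars at 5% vs 10% with the weakest link) to decisive (0.21 stars at 5% vs 25% with the strongest).

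A reader might infer that hypothesis 4 will be answered with the wrong sign. The documents do not support that. The table shows false positives when true ratings are equal. A reversal needs further assumptions: in the second model, an SSI truly 0.10 SD worse, with 20% vs 5% dropout, would appear 0.02 SD better (ρ = 0.5) or 0.09 SD better (ρ = 0.8). With no dropout rate in the documents, this is a possibility and not a prediction.

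The point merits a cheap, pre-specified addition to a secondary analysis.

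**What to change.** The Data Collection section says recruitment has not begun, so the change can be pre-specified. In Secondary analyses, item 4:

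- **(a)** Compare in-session SSI completion, among all randomised, between each experimental SSI and the active comparison. Report it beside CEQ, stars and Aha! rate.
- **(b)** Label the rating comparison as conditional on having given a rating.
- **(c)** Add a missing-not-at-random sensitivity analysis for non-finishers, run whether or not the attrition test is significant. Use a delta-adjusted or tipping-point range, with the lowest score (or no Aha! moment) as its extreme bound.

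Report (c) as a range, and do not let the lowest-score bound veto a claim. That bound penalises exits unrelated to acceptability. At 5% vs 15% dropout unrelated to rating, where the planned analysis is unbiased, it shifts the difference by (3.66 − 1) × (0.15 − 0.05) = 0.27 stars against the SSI and falsely rejects 94% of the time.

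It would also help to state in the plan whether attrition includes in-session exit and whether acceptability is asked again at week 4.

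The cost is some SAP wording, a few extra regressions on data already to be collected, and a more cautious reading of acceptability differences.

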Robustness Check: Researchers will not correct for multiple hypotheses in primary and secondary analyses because each test of an intervention's effect is viewed as a separate hypothesis. However, it might be that some statistically significant results detected are false positives that occur due to testing so many hypotheses at once. To examine this possibility, researchers will conduct a robustness check that replicates all analyses that compare an outcome across many conditions correcting for multiple hypotheses using the Benjamini-Hochberg procedure (Benjamini & Hochberg, 1995).

Inference Criteria: P-values will be used as the criterion for statistical significance. Two-sided tests will be used for all analyses. Effects of $p \leq .05$ will be reported as significant, $.05 < p \leq .1$ as marginally significant, and $p > .1$ as nonsignificant.

Missing data handling: Because participants can choose to skip items, there may be some missing data within outcome measures. If one's response to a scale is missing 33% of its items or fewer, researchers will impute a value for each missing item using the mean of the other items of the scale that the participant answered.

If an outcome scale is missing more than 33% of its items, researchers will consider the entire scale to be missing. In these cases, researchers will not impute missing outcome data because linear mixed models' estimates for longitudinal clinical trial data are not improved by outcome data imputation (Chakraborty & Gu, 2009). Researchers will impute missing covariate data as described in the cleaning script (<https://osf.io/jpk38>).

Sample Size: Researchers will aim to recruit 500 participants per intervention condition, except that the passive control condition will have 3X as many participants as the other conditions because it will improve the statistical power of analyses comparing conditions to the passive control. Thus, researchers aim for a total baseline sample size of $n = 7,500$. This sample size will enable us to detect change in depressive symptoms from baseline to follow-up between each intervention condition and the passive condition with an effect size smaller than Cohen's $d = 0.17$, with 90% power and alpha = 0.05. This sample size will also allow us to detect differences in change in depressive symptoms from baseline to follow-up between each intervention condition smaller than $d = 0.19$.

References:

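### Must the hypothesis-5 model adjust for baseline PHQ-9 to keep regression to the mean from producing a false result?

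*Combined protocol and SAP*

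**What the plan says.** Secondary hypothesis 5 states that "participants who expect they can improve their depression more at baseline will show a different change in depressive symptoms" over the four weeks. It names no direction and does not claim that expectancies predict outcome beyond starting severity. The Inference Criteria add: "Two-sided tests will be used for all analyses".

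The matching item under Secondary analyses fits a mixed model with "depressive symptoms as the DV, timepoint, baseline depression expectancies, and the interaction between the two as predictors", and with "a participant identifier nested in experimental condition as a random intercept". Baseline PHQ-9 is a row of the outcome, not a predictor. The two covariate-adjusted sensitivity analyses re-run the primary analysis only, and neither lists baseline PHQ-9.

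On entry, the Inclusion criteria say: "They must also score at least 10 on the PHQ-9 screen". The text does not say whether this screening score also serves as the baseline PHQ-9; the linked timepoints document was not available.

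**The concern.** Expectancies are self-reported in the same session as the baseline measures and are not randomised, so nothing balances initial severity across their levels. If more depressed people hold lower expectancies, they start higher and, on remeasurement, tend to fall further. The timepoint-by-expectancy term could then be non-zero although expectancies say nothing about week-4 depression once baseline PHQ-9 is known. Everyone is selected on a high score, and the whole sample, planned at 7,500, enters one test, so even a weak association could reach p ≤ .05. A reader might conclude that pessimistic participants benefit more, or a real advantage of positive expectancies might be hidden. The random intercept does not prevent this.

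**Working it through.** **The plan's own figure.** The Sample Size section gives 12 × 500 + 1,500 = 7,500, and d below 0.17 for 500 against 1,500 "with 90% power and alpha = 0.05". The detectable d is (1.960 + 1.282) × √(1/500 + 1/1,500) = 3.242 × 0.0516 = 0.167, so the figure reproduces. The plan states no figure for hypothesis 5.

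**Assumed inputs.** The documents do not give the correlation r between expectancy and baseline PHQ-9, the PHQ-9 stability ρ from baseline to week 4, the PHQ-9 SD, or retention. The ranges used are r from 0 to -0.4, ρ from 0.5 to 0.9, SD 5.5, and 5,250 (30% dropout) or 6,000 (20% dropout) at week 4. The formulas use standardised variables.

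**1. What the term estimates.** With complete baseline and week-4 pairs, the week-4 interaction coefficient is the slope of change (y4 - y0) on expectancy E, that is, Cov(E, y4) - Cov(E, y0). This is the quantity in hypothesis 5.

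**2. The scenario behind the concern.** Suppose week-4 PHQ-9 depends on E only through observed baseline: E[y4 | y0, E] = ρ·y0. Then

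- slope = (ρ - 1)·r
- Var(change | E) = 2(1 - ρ) - slope²
- z = slope × √6,000 / SD(change | E)

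For r = -0.1:

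| ρ | slope | z | chance of p ≤ .05 |
|---|---|---|---|
| 0.5 | 0.05 | 3.88 | 97% |
| 0.6 | 0.04 | 3.47 | 93% |
| 0.7 | 0.03 | 3.00 | 85% |

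For r from -0.2 to -0.4, z runs from 6.0 to 15.8. The arithmetic is right, but it does not show an inflated error rate. In this scenario mean change really does differ by (ρ - 1)·r per SD of expectancy, so the hypothesis-5 null is false and rejecting it is correct. The 5% benchmark belongs to a different null: no association with week-4 PHQ-9 given baseline PHQ-9.

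**3. A second mechanism, equally compatible with the documents.** Suppose E follows the stable part of symptoms and not the momentary part of the baseline score. Then Cov(E, y4) = Cov(E, y0), and the raw-change slope is 0 whatever r is.

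**4. The entry threshold.** The table gives rejection rates for the raw-change test with 5,250 completers and ρ or reliability 0.7. The first row is closed form. The others are simulations of 150 runs per setting, using least squares on change scores; the mixed model itself was not fitted. The value of r is before selection, and E has no effect of its own.

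| E follows | Threshold applied to | r = -0.1 | r = -0.3 | Sign of slope |
|---|---|---|---|---|
| observed baseline score | not modelled | 80% | about 100% | positive |
| observed baseline score | the baseline score itself | 11% to 33% | 71% to 96% | positive |
| stable level | not modelled, or a separate screening score | 1% to 7% | 3% to 7% | none |
| stable level | the baseline score itself | 46% to 53% | 100% | negative |

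A positive slope means that higher expectancy goes with a smaller fall. The negative slopes in the last row are -0.11 to -0.37 PHQ-9 points per SD. At r = 0, rejection is 3% to 7% throughout. With ρ = 0.9 and no threshold, it is 37% at r = -0.1 and 90% at r = -0.2. So neither significance nor direction follows from the design.

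**5. The alternative of adjusting for baseline PHQ-9.** In the first mechanism this returns rejection to 4% to 8% at r = -0.3. In the second, the partial slope is r(1 - ρ)/(1 - r²):

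- r = -0.1, ρ = 0.7: -0.03/0.99 = -0.030 SD, z = -3.3 at 6,000
- r = -0.3, ρ = 0.5: -0.15/0.91 = -0.165 SD, z = -14.3 at 6,000

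Simulation under the second mechanism at r = -0.3 agrees: adjusted rejection is 100%, with slopes of -0.41 to -0.54 points per SD although E has no effect of its own. Adjusting for a baseline score that contains error leaves residual confounding by stable severity.

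**The case for a change.** The best counter-argument is that the second mechanism is fragile. Screening, consent and the baseline questionnaire follow one another at once, so a shared momentary mood is plausible. If E correlates by c with only the transient part of baseline PHQ-9, the correlation of E with change is -c/√2. With 5,250 completers, c = -0.055 gives z = 0.055 × 0.707 × 72.5 = 2.82 and about 80% rejection; c = -0.1 gives 99.9%. These rates do not depend on reliability. Because the hypothesis has no direction, either sign would count as support. No planned sensitivity analysis shows how far the result depends on starting severity, and the Benjamini-Hochberg check concerns comparisons across conditions.

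This stands as a caution on interpretation. A significant interaction should not be read as a prognostic or causal effect of expectancies independent of baseline severity. The plan does not make that claim, however, and in this case too the raw change differs as the hypothesis says. Reporting the correlation of expectancy with baseline PHQ-9, or showing an adjusted analysis beside the planned one, would help a reader. That would be an optional addition, not the repair of an error.

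**Conclusion.** The concern does not hold. The planned interaction tests the registered question: a two-sided association between expectancies and raw PHQ-9 change. Rejection rates of 85% to 97% at r = -0.1 are power against a real difference in raw change of 0.03 to 0.05 SD, not false positives. They rest on an assumed correlation, an assumed stability, no modelling of the entry threshold, and expectancy tracking the observed baseline score. Under other assumptions the documents equally allow, the slope is zero or has the opposite sign. Choosing between change scores and baseline adjustment for a non-randomised predictor is a choice of estimand (Lord's paradox), and neither is free of bias under every mechanism. Replacing the model would exchange one possible artefact for another, of -0.03 to -0.165 SD for r from -0.1 to -0.3 and stability 0.5 to 0.7. Hypothesis 5 is secondary, and no comparison between randomised conditions is affected. The linked analysis script was not available, so this rests on the model as the SAP describes it.

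### Secondary analysis 6 weights each SSI roughly by its retained participants; an equal-weighted contrast from the models already planned would fix the average at almost no cost

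*Combined protocol and SAP*

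**What the plan says.** - **Target.** Secondary Hypotheses, item 6: "We hypothesize that, on average, the SSIs will be more effective at improving all well-being outcomes" than the passive control, from baseline to week 4 or to post-test. No weights are given for the average.
- **Analysis.** Statistical Analysis Plan, Secondary analyses, item 6: the main model is re-run with condition "re-coded into a two-level factor in which any of the 12 active SSIs will be coded as" active. The random part is described as follows: "The random intercept, participant ID will be nested within experimental condition". No term lets the change over time differ among the SSIs.
- **Allocation.** Design: participants are assigned "with even odds of allocation, except that the passive control condition will have 3X odds of allocation". Sample Size: "Researchers will aim to recruit 500 participants per intervention condition", with three times as many in passive control and 7,500 in total.
- **Missing outcomes.** Missing data handling: when more than a third of a scale is missing, the whole scale is treated as missing and is not imputed, because the analysis relies on the mixed model.
- **Attrition.** Sensitivity analyses, item 3: attrition is tested across conditions. If it differs, the primary and secondary analyses are re-run with inverse probability weighting.

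**The concern.** At randomisation each SSI makes up 1/12 of the active group. In the two-level model the active group has one common change from baseline, and it is estimated from whoever is still observed. An SSI that loses more people contributes less to that change. A participant nested in condition may have a different level, but does not get an arm-specific change.

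This also weakens the plan's reason for not imputing. A mixed model protects against dropout that is explained by terms in the model. In the 13-level primary model, arm is such a term. In item 6 it is not, so dropout that depends on arm is no longer accounted for when effects also differ by arm.

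The stake is the value of one secondary estimate per outcome and timepoint. It is pulled up if the weaker SSIs lose more users and pulled down if the stronger ones do. The pull reflects retention, not how well the SSIs work.

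**Working it through.** **1. The plan's own figures.** 12 × 500 + 1,500 = 7,500. The detectable difference for one SSI against passive control is (1.960 + 1.282) × √(1/500 + 1/1500) = 0.167, which agrees with the stated value below 0.17 at 90% power. The Sample Size section gives no figure for hypothesis 6 and no retention rate.

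**2. Weight of each SSI in the planned estimate.** Take two timepoints, a random intercept and equal arms. The estimated week-4 active mean is the completers' week-4 mean, plus an adjustment for the completers' baseline difference from everyone randomised. If dropout within an arm is unrelated to baseline, that adjustment has expectation zero. The weight of SSI k is then

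w_k = r_k / Σ r_j, where r_k is its week-4 retention.

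Solving the generalised least squares equations gives the same weights at intraclass correlations of 0.5 and 0.7.

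**3. Assumed inputs (not in the documents).** True effects evenly spaced from 0 to 0.30 SD across the 12 SSIs (equal-weighted mean 0.150). Retention evenly spaced over the stated range and perfectly ordered with effect. Baseline to week-4 correlation 0.5.

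At 60% to 90% retention the weights run from 0.60/9.0 = 0.0667 to 0.90/9.0 = 0.1000, against 1/12 = 0.0833.

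**4. Shift.** Shift = cov(r, effect) / mean(r). For 12 evenly spaced values the covariance is (range of r) × (range of effect) × 11.917/121. At 60% to 90%: 0.30 × 0.30 × 11.917/121 = 0.00886, and 0.00886/0.75 = 0.0118.

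| Assumed SSI retention | Target if retention rises with effect | Target if it falls | Shift (SD) |
|---|---|---|---|
| equal | 0.150 | 0.150 | 0 |
| 80–90% | 0.154 | 0.147 | 0.0035 |
| 70–90% | 0.157 | 0.143 | 0.0074 |
| 60–90% | 0.162 | 0.138 | 0.0118 |
| 50–90% | 0.167 | 0.133 | 0.0169 |

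A simulation with control retention of 80% gave 0.162 and 0.137 at 60% to 90%, with a standard error of about 0.031. The equal-weighted contrast stayed at 0.149 to 0.151. For scale, √(1/6000 + 1/1500) = 0.029 with no loss, and 0.032 at 80% retention throughout. So 0.0118/0.031 is about 0.4 SE.

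**5. Closer to the planned model (60% to 90% retention).**
- *Three timepoints, all week-4 dropouts with post-test data, effect the same at both times.* Weights run from 0.0722 to 0.0944 (ratio 1.31 instead of 1.50). The spread is 0.0222 instead of 0.0333, so the shift is about 0.0118 × 0.0222/0.0333 = 0.008 SD, or 0.008/0.031 = 0.25 SE.
- *Three timepoints, no effect at post-test.* The ratio stays at 1.50.
- *Two timepoints, with a random intercept for the 13-level condition added (assumed variance 0.02).* The ratio is 1.40.

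**6. The planned safeguard.** Weighting completers by 1/retention brings every SSI back to 0.083–0.084. Whether the re-run happens depends on detecting differential attrition. With passive retention of 82.5%, a 13-arm chi-square test at 5% has about 52% power if SSI retention spans 80–85%, and over 99% if it spans 75–85%.

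**7. Precision of equal weighting (60% to 90%).** The SE of the active mean is √(Σ 1/n_k / 144) = 0.0150 with equal weights and √(1/Σ n_k) = 0.0149 with completer weights.

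**The case against.** The case against is substantial, and much of it stands.

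- **The plan has a remedy.** A reader might infer that differential attrition is ignored. It is not: the inverse-probability-weighted re-run covers secondary analyses, so it covers item 6. Where the trigger might miss, little is lost. For retention of 80–85% the largest shift is 0.05 × 0.30 × 11.917/121 / 0.825 = 0.0018 SD, about 0.06 SE. What remains is that for wider spreads the re-run is a sensitivity analysis beside a main estimate that is still tilted.
- **The sizes are upper bounds.** They assume that retention and effect are perfectly ordered. The shift scales with their correlation. At 60% to 90% retention, a correlation of 0.3 gives 0.3 × 0.0118 = 0.0035 SD (0.11 SE), and random pairing gives a median absolute shift of 0.0025 SD. Nothing in the documents links the two.
- **Conclusions would rarely change.** With a mean of 0.150 and an SE of 0.031, power is 99.8%. At the worst shift for 50–90% retention it is still 99.0%. A reader might infer a general false-positive problem. If no SSI has any effect, or all have the same effect, the shift is exactly zero. Only if effects spread over 0.30 SD cancelled to a true average of zero would a 5% test reject more often, about 6.7% at 60–90% retention and 8.5% at 50–90%, again with perfect ordering and two timepoints.
- **No contradiction in the text.** A reader might infer that the recode contradicts hypothesis 6. It does not, because the hypothesis names no weights. Equal weighting is what equal allocation among the SSIs suggests, but the plan does not require it.

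**Conclusion.** The point holds as a minor matter of defining the average. The two-level recode weights each SSI roughly by its retained participants, and the plan does not say that this is intended. The weighting is exactly proportional to completers in the two-timepoint model. It can be softened by post-test data or an arm-level intercept, but neither removed it in the cases examined. The same mechanism applies to the post-test estimate through those who leave during the session; no size was calculated for that.

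Under the assumed 0 to 0.30 SD effects and 60% to 90% retention, the upper bound is about 0.012 SD (0.4 SE), or 0.008 SD (0.25 SE) in the three-timepoint case with full post-test data. All retention and effect spreads are assumptions.

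A reader might take this as a threat to the trial's main result. The documents do not support that. Hypothesis 6 is the last of six secondary hypotheses, and the primary comparisons of each SSI with passive control use the 13-level factor and are untouched.

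**What to change.** In Secondary analyses, item 6, keep the 13-level condition factor. Define the average SSI effect as the linear contrast that gives 1/12 to each of the 12 timepoint-by-condition coefficients, with passive control as reference. Take it from the model already planned for each outcome, at week 4 and, where the outcome is collected then, at post-test. Show the two-level recode as a supplement. If weighting by completers is intended instead, say so.

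The contrast settles only the weights among SSIs. Sensitivity analysis 3 should stay as planned for other effects of attrition.

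Cost: one sentence in the SAP and one contrast statement per fitted model. No new data are needed, and the loss of precision is negligible (0.0150 against 0.0149 for the active mean; the simulated SE of the full contrast agreed with the pooled one to within 0.0002).
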